5.4.2.3 Cumulative Corticosteroid (CS) Usage

Cumulative corticosteroid (CS) usage per patient (mg) will be presented by treatment period (up to first 12 weeks, after first 12 weeks, entire treatment period and follow-up period), by dose level and overall in a table. To calculate this endpoint, the following steps will be followed:

Step 1: Select CSs with route = “ORAL” or “INTRAVENOUS”. The CSs will be converted into prednisolone/prednisone dosage equivalent using the below conversion chart.

CS medication	Conversion factor
Prednisone, Prednisolone	1
Hydrocortisone	0.25
Methylprednisolone, Methylprednisolone Sodium Succinate	1.25

Dexamethasone, Betamethasone	6.67
------------------------------	------

Step 2: The CSs usage will be converted to standard frequency using the following conversion chart.

Frequency	Unit	Conversion factor
QD, Q24H, ONCE, CONTINUOUS, BD PRN, PRN	mg	1
5 TIME A DAY	mg	5
QID	mg	4
TID	mg	3
2-3 DAILY	mg	2.5
BID	mg	2
QOD, EVERY 2 DAYS	mg	1/2
BIS	mg	2/7
QS, EVERY WEEK	mg	1/7
Any value	mg/day	1

Once the prednisolone/prednisone dosage equivalent and frequency are converted as above, each record of CSs taken will be converted to prednisolone with standard frequency (mg/day).

Step 3: The duration for each record of CS taken will be calculated using the formula: Duration = CS end date – CS start date + 1, in days. Any partial start or end date of CSs taken will be imputed using the algorithm specified in Section 3.5.1. If the CS start date is completely missing, then the date will be imputed as Week 1 Day 1, i.e. it is assumed that the medication is taken at the study entry. If the CS stop date is completely missing, then the date will be imputed as Date of End of Study, i.e. it is assumed that the medication is taken up to the end of study.

If the CS start date is before the Week 1 Day, then the CS start date will be replaced by the Week 1 Day 1; if the CS start date is after the date of Week 29 (Day 197) - 1, this record will not be used to summarize cumulative dose for CSs.

If the CS end date is after the date of Week 29 (Day 197) - 1, then the CS end date will be replaced by the date of Week 29 (Day 197) - 1; if the CS end date is before the study treatment start date, this record will not be used to summarize cumulative dose for CSs.

Note that above date adjustments only apply to cumulative CS dose calculation. Other analyses, where CS dose is needed, will use CS start and end dates as reported.

Step 4: The “record” level cumulative CSs usage will be calculated as: record level cumulative dose = prednisolone/prednisone dosage equivalent * conversion factor for frequency * duration (days).

Step 5: The patient level cumulative CSs usage will be calculated as the summation of all the non-missing record level cumulative doses. If a patient had no CS records that meet the above criteria, the CS

cumulative dose is set as 0. The average daily CS usage in mg/day will be calculated as the cumulative doses divided by the number of days within a study period.

All CS usage will be presented in a listing showing record level prednisone dosage equivalent (mg), dose, frequency, route, start and stop dates. The total prednisone dosage equivalent in mg/kg will also be calculated by using the last measured weight prior to the current visit.

5.4.2.4 CS Dose on the Day Before Each Visit

For each patient on the day before each scheduled visit, dosage level of CS dose in mg/day and mg/kg/day will be summarized using summary statistics by dose level and overall. Types of CS other than prednis(ol)one are converted to dose-equivalent prednis(ol)one (see Section 5.4.2.3).

For Screening and Week 1/Day 1 visits, however, the CS dose is set as the day of, rather than the day before.

If a patient did not report any CS, then the dosage level is set as 0. If a subject is terminated prior to a visit, then this subject is not included in the calculation for visit.

The same table will be repeated for: 1) patients achieved at least one CDA and 2) to included patients achieved at least one.

A listing of the CS dose in mg/day and mg/kg/day will be listed with the CDA and CR response at each visit. Change from Baseline in PDAI ABSIS, ABQOL and TABQOL Scores

Quantitative assessment of patient response and disease progression will be determined using the following scores at visits specified in the Schedule of assessments (Table 1):

- 1) Pemphigus Disease Area Index (PDAI) score – Total Activity Score
- 2) Pemphigus Disease Area Index (PDAI) score – Total Damage Score
- 3) Autoimmune Bullous Skin Disorder Intensity Score (ABSIS) score
- 4) Autoimmune Bullous Disease Quality of Life (ABQOL) score
- 5) Treatment of Autoimmune Bullous Disease Quality of Life (TABQOL) score

The PDAI questionnaire has two components including activity and damage. The activity component consists of skin, scalp and mucosa parts and the damage component consists of skin and scalp parts. Actual values, change from screening, percent change from screening, change from baseline and percent change from baseline in PDAI total activity, total damage scores will be summarized by dose level and overall, respectively.

The PDAI activity or damage total scores per body part will be calculated as the sum of the scores on that body part as follows. PDAI total activity and total damage scores will be calculated as follows:

- PDAI total activity score = Total skin activity + Total scalp activity + Total mucosa activity
- PDAI total damage score = Total skin damage + Total scalp damage

The ABSIS questionnaire has three components, including skin involvement, oral involvement and (oral) severity. The ABSIS scores will be calculated separately for each component. The ABSIS total activity score and total ABSIS score will also be calculated as follows:

- Skin involvement total score = sum of (%BSA * Weighting factor for each skin involvement area)
- Oral involvement total score = sum of (score from each oral part)
- (Oral) Severity total score = sum of (Level * Factor of discomfort for each food item)
- ABSIS total activity score = Skin involvement total score + Oral involvement total score
- Total ABSIS score = Skin involvement total score + Oral involvement total score + Severity total score

Actual values and change from baseline in ABSIS skin involvement total score, ABSIS oral involvement total score and ABSIS total activity score will be summarized for all patients, and for the two sub-groups:

- baseline oral involvement total score = 0 vs. >0
- baseline skin involvement score = 0 vs >0.

When calculating skin involvement total score, if %BSA = 0, then skin involvement score component is 0. If %BSA > 0, then weighting factor needs to be considered, and if weighting factor is missing in this circumstance, then the skin involvement total score and ABSIS total score are considered missing.

The ABQOL and TABQOL questionnaires both contains 17 questions with numerical scores. The ABQOL and TABQOL scores will be calculated as the sum of scores from each question. Actual values and change from baseline in ABQOL and TABQOL scores will also be summarized by dose level and overall in a table. If individual scores are missing, then the total scores are set as missing.

PDAI, ABSIS, ABQOL and TABQOL scores and sub-scores (for PDAI and ABSIS) by patient and visit will be presented in separate listings.

5.4.2.5 Change from Baseline in Simple Nutritional Appetite Questionnaire (SNAQ) score

Simple Nutritional Appetite Questionnaire (SNAQ) contains 4 questions with numerical scores and is assessed at visits specified in the Schedule of assessments (Table 1). The SNAQ score will be calculated as the sum of scores from each question. The SNAQ score ranges from 4 to 20. If individual scores are missing, then the total score is set as missing.

Actual values and change from baseline in SNAQ score at each visit will be summarized by dose level and overall.

The SNAQ score will be presented in a listing by patient and visit.

5.4.2.1 *Change from Baseline and Percent Change from Baseline in Total Anti-DSG, Anti-DSG 1 and Anti-DSG 3*

The Anti-DSG 1 and Anti-DSG 3 results are measured at visits specified in the Schedule of assessments (Table 1). Total Anti-DSG is the sum of Anti-DSG 1 and Anti-DSG3, where at least one of Anti-DSG 1 or 3 is positive per Section 5.1.3, i.e. Anti-DSG 1 \geq 14 and/or Anti-DSG 3 \geq 9.

Actual result, change from baseline and percent change from baseline in Total Anti-DSG, positive Anti-DSG1, i.e. \geq 14, and positive Anti-DSG 3, i.e. \geq 9, at each visit will be summarized by dose level and overall. The same descriptive statistics will be produced by baseline Anti-DSG value (\geq 100 units vs. $<$ 100 unit).

The Total Anti-DSG, Anti-DSG 1 and Anti-DSG 3 values will be presented in a listing by patient and visit.

5.5 Safety Analyses

The Safety Population will be used for the safety analyses. The summary statistics will be done by dose level and overall for all study visits, unless specified otherwise. Patient data listings will be listed by starting dose, patient, dose level and study visit or start date of event if applicable.

5.5.1 Adverse Events

TEAEs will be attributed to the dose level where the adverse event start date is on or after the start date of that dose level and before the next dose level if applicable.

Adverse events with preferred term (PT) = “Pemphigus” will be excluded from the TEAE tables. All pemphigus PT are Disease Under Study and will be documented in a separate summary table and a separate patient data listing labeled as Disease Under Study Events.

A summary of adverse events by dose level and overall will include:

- The number of pre-treatment AEs and the number/percentage of patients reporting at least one pre-treatment AE
- The number of pre-treatment SAEs and the number/percentage of patients reporting at least one pre-treatment SAE
- The number of TEAEs and the number/percentage of patients reporting at least one TEAE
- The number of post last dose adverse events and the number/percentage of patients reporting at least one post last dose adverse event
- The number of related TEAEs and the number/percentage of patients reporting at least one related TEAE
- The number of serious TEAEs and the number/percentage of patients reporting at least one serious TEAE
- The number of related serious TEAEs and the number/percentage of patients reporting at least one related serious TEAE

- The number of TEAEs leading to study discontinuation and the number/percentage of patients reporting at least one TEAE leading to study discontinuation
- The number of deaths and the number/percentage of patients reporting at least one TEAE death
- The number/percentage of patients reporting TEAEs by Action Taken with Study Drug
- The number/percentage of patients reporting TEAEs by the maximum grade

TEAEs will be summarized by SOC and PT by dose level and overall. Patients with multiple events within a particular SOC or PT within each dose level will be counted once within that dose level. The number of episodes of events for each SOC and PT will also be displayed. The same tabulation will be performed for related TEAEs, SAEs and AE leading to study drug discontinuation.

TEAEs will also be summarized by the maximum intensity grade (Grade 1 to 5), SOC and PT. Patients with multiple events within a particular SOC or PT will be counted once under the maximum intensity grade. The same tabulation will be performed for related TEAEs.

Patient data listings will be generated for:

- Prior adverse events
- Prior SAE
- TEAEs
- Related TEAEs
- SAEs
- TEAE leading to study drug discontinuation
- TEAE leading to death (AE with intensity = Grade 5 – Death related AE)
- Post last dose TEAEs
- Disease Under Study (Pemphigus PT events)

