2.3 Overall Risk/Benefit Assessment

Design summary: Study PRN1008-005, is a Phase 2, open-label, cohort study of 12 weeks of PRN1008 therapy, followed by 12 weeks of follow up, using a starting dose in **Part A** of 400 mg twice a day (*bid*), with intra-patient dose-escalation to a maximum dose of 600 mg twice a day. In **Part B** the starting dose is 400 mg once daily (*qd*) with intra-patient dose-escalation to 400 mg *bid* allowed at or after the week 3 visit based upon insufficient clinical response (and then again to 600 mg *bid* if necessary at or after the Week 5 visit).

Safety Profile: The one patient with a related SAE of cellulitis and fever observed in a patient with a higher risk of infection underscores the likely, mechanism-based risk of infection during chronic treatment with a BTK inhibitor.

Based on data from 21 patients in this Study PRN1008-005, as of January 18, 2018, PRN1008 has been well tolerated using the IR tablet formulation in doses of up to 400 mg *bid* (n=19), 500 mg *bid* (n=1) and 600 mg *bid* (n=1). No patients have discontinued PRN1008 therapy or dose-reduced due to treatment-related adverse events.

Efficacy: High clinical response rates have been observed in the first 21 PV patients in this study, on a background of zero or low dose CS, using a starting dose of 400 mg *bid*. It is possible that a lower, once daily dose may have a greater benefit-risk relationship, and this is being explored in **Part B**.

Risk/Benefit: Given the encouraging safety and efficacy profile of PRN1008, further exploration of minimally effective dose levels and longer durations of therapy is justified in pemphigus patients. The results of this study will be used to guide PRN1008 use in future patient studies. No risks other than those previously mentioned in the Investigator's Brochure or in the summary of PRN1008 clinical experience described above are known at this time. Refer to [PRN1008 Investigators' Brochure](#), Section 5.6.2, for additional information.

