3 OBJECTIVES OF THE STUDY

3.1 Primary Objectives

- To evaluate the clinical safety of PRN1008 in patients with PV over a 12-week (**Part A**) or 24-week (**Part B**) treatment period
- To evaluate the clinical activity of PRN1008 in patients with PV, per criteria in the European Academy of Dermatology and Venereology (EADV) 2014 Pemphigus S2 Guideline ([Hertl et al. 2015](#))*

*As modified to define CR without 2-month durability definition

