11 STATISTICAL METHODS AND DETERMINATION OF SAMPLE SIZE

11.1 Primary Outcome Measures

11.1.1 Safety

The incidence of treatment-emergent AEs (TEAEs), including clinically significant changes in physical examination, laboratory tests, and vital signs.

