9.1. Adverse Events

An AE can be any unfavorable and unintended sign (including an abnormal laboratory finding, for example), symptom, or disease temporally associated with the use of an investigational product, whether or not considered related to the product. All AEs encountered during the study will be reported in detail in the CRF, begins at the time of the first screening/eligibility assessment and ends at the end of the study for each patient. Pre-existing conditions that worsen during a study are to be reported as AEs. Clinically significant changes in physical examination, laboratory safety tests, and vital signs will also be defined as AEs and recorded appropriately. All AEs will be coded using the MedDRA Dictionary (MedDRA, Version 18.0).

Imputation for missing AE onset dates and end dates can be found in Appendix 15.4.

A treatment-emergent AE (TEAE) is defined as an AE that begins on or after the first dose of study drug.

If the AE onset date is missing after imputation and the imputed end date is on or after the first dose of study drug, or if onset date and end date are both missing, then the AE will be classified as a TEAE. If the imputed AE onset date is the same as the first dose of study drug, and AE onset time on or after the first dose of study drug or AE onset time is missing, then the AE will also be classified as a TEAE.

An overall summary of the number and percentage of patients with any TEAE, serious TEAE, study drug-related TEAE, study drug-related serious TEAE, TEAE leading to treatment discontinuation, and AEs leading to death will be provided overall and by maximum dose level.

All AEs will be presented in a listing for the Safety Population.

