2.2 Study Design

This is a Phase 2, open-label, pilot cohort study to evaluate the safety, clinical activity, pharmacodynamics, and pharmacodynamics of PRN1008 in patients with newly diagnosed or relapsing PV. An open-label design was chosen for several reasons: PV does not spontaneously remit so there is no placebo effect to account for; clinicians need to know when to use rescue CSs, if necessary, in a timely manner; and lastly, the pilot nature of the investigation itself is best explored in an open-label fashion.

Up to 28 days before enrollment in the study, patients will be required to sign an informed consent form, after which screening assessments will be carried out. Patients must fulfill all entry criteria to be enrolled into the study. Patients who fail to meet the entry criteria may be rescreened at the discretion of the Investigator. Up to 25 male or female patients with newly diagnosed (i.e., naïve to an effective induction treatment regimen) or relapsing, biopsy-proven, mild or moderate PV patients (Pemphigus Disease Activity Index [PDAI] 8 to 45) to enrolled into each parts of the study.

In Part A, the initial dosing was 400 mg twice daily (bid). The duration of study therapy was 12 weeks starting on Day 1 and ending on study Day 84 (total duration of individual subject participation is 28 weeks), with follow-up visits (off-treatment) until Week 29.

In Part B, the initial dosing is 400 mg once daily (qd), with intra-patient dose escalation to 400 mg bid allowed at or after the Week 3 visit for insufficient clinical response (and then again to 600 mg bid if necessary at or after the Week 5 visit). The duration of study therapy is 24 weeks starting on Day 1 and ending on study Day 169, with a follow-up visit (off-treatment) on Day 197 (Week 29). The total duration of individual subject participation is approximately 32 weeks.

Dose Escalation Rules Part B

Current Dose	Inadequate Clinical Response* Dose-Escalation Rules
400 mg qd	Increase to 400 mg bid (allowed at Week 3 visit or later)**
400 mg bid	Increase to 600 mg bid (allowed at Week 5 visit or later)**
600 mg bid	No dose increase possible.

* Investigator discretion: Generally, clinical response is shown by some improvement seen in first 2 weeks with CDA achieved by the Week 5 visit

** Unless tolerability issues preclude dose-escalation

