Study drug treatment information will be summarized and documented in the ITT and mITT Population. Number of dose adjustments and maximum dose will be tabulated by starting dose. Descriptive statistics for study drug exposure and compliance will be done by dose level and overall. Patient data listings will be listed by starting dose and patient and study visit.

5.3.1 **Study Drug Exposure**

Study drug exposure will be summarized by dose level.

- Duration of exposure for Dose level i (days) =
(date of last dose for dose level i – date of first dose for dose level i) + 1.
- Dose Taken for Dose level i (mg) = (Number of tablets dispensed – Number of tablets returned)*
Current Dose Level (mg)
- Calculated Dose for Dose level i (mg/day) =
(Dose taken for Dose level i)/Duration of exposure for Dose level i.

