Table B.14.2.2.51.2 Anti-DSG 3 – Actual Values, Change and Percent Change from Baseline – Overall and by Baseline Value (Completer Population)

Table B.14.2.2.51.3 Anti-DSG 3 – Actual Values, Change and Percent Change from Baseline – Overall and by Baseline Value (PP Population)

Table B.14.3.1.1 Summary of Adverse Events (Safety Population)

	400 mg QD (N = n)	400 mg BID (N = n)	600 mg BID (N = n)	Post Last Dose (N = n)	Overall (N = n)
Number of Pre-treatment AEs					x
Number (%) of patients with at least one Pre-treatment AE					x (x.x)
Number of Pre-treatment SAEs					x
Number (%) of patients with at least one Pre-treatment SAE					x (x.x)
Number of Treatment Emergent Adverse Events (TEAE)	x	x	x	x	x
Number (%) of patients with at least one TEAE	x (x.x)	x (x.x)	x (x.x)	x (x.x)	x (x.x)
Number of Related TEAEs	x	x	x	x	x
Number (%) of patients with at least one Related TEAE	x (x.x)	x (x.x)	x (x.x)	x (x.x)	x (x.x)
Number of Treatment Emergent SAEs	x	x	x	x	x
Number (%) of patients with at least one Treatment Emergent SAE	x (x.x)	x (x.x)	x (x.x)	x (x.x)	x (x.x)
Number of Related Treatment Emergent SAEs	x	x	x	x	x
Number (%) of patients with at least one Related Treatment Emergent SAE	x (x.x)	x (x.x)	x (x.x)	x (x.x)	x (x.x)
TEAE - Action taken with study drug – Number (%) of patients*					
Dose not changed	x (x.x)	x (x.x)	x (x.x)	x (x.x)	x (x.x)
Dose reduced	x (x.x)	x (x.x)	x (x.x)	x (x.x)	x (x.x)
Study drug interrupted	x (x.x)	x (x.x)	x (x.x)	x (x.x)	x (x.x)
Study drug discontinued	x (x.x)	x (x.x)	x (x.x)	x (x.x)	x (x.x)

Table B.14.3.1.1 Summary of Adverse Events (Safety Population)

	400 mg QD (N = n)	400 mg BID (N = n)	600 mg BID (N = n)	Post Last Dose (N =n)	Overall (N = n)
Not applicable	x (x.x)	x (x.x)	x (x.x)	x (x.x)	x (x.x)
Unknown	x (x.x)	x (x.x)	x (x.x)	x (x.x)	x (x.x)
TEAE - Maximum Intensity of TEAE – Number (%) of patients					
Grade 1	x (x.x)	x (x.x)	x (x.x)	x (x.x)	x (x.x)
Grade 2	x (x.x)	x (x.x)	x (x.x)	x (x.x)	x (x.x)
Grade 3	x (x.x)	x (x.x)	x (x.x)	x (x.x)	x (x.x)
Grade 4	x (x.x)	x (x.x)	x (x.x)	x (x.x)	x (x.x)
Grade 5	x (x.x)	x (x.x)	x (x.x)	x (x.x)	x (x.x)

Patients are classified into different dose levels according to the dose they received at the start of AE.

Percentages are based on the number of patients in each dose group and overall.

Adverse events where PT='Pemphigus' are excluded from this table.

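### By-dose adverse event percentages in Part B ignore unequal time at each dose, and Part A counts the 12 off-drug weeks as treatment-emergent

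*SAP*

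**What the plan says.** The primary safety outcome (Protocol 11.1.1) is "The incidence of treatment-emergent AEs (TEAEs), including clinically significant changes in physical examination, laboratory tests, and vital signs". No time-at-risk denominator is named.

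**Part B.** SAP 5.5.1 attributes events by dose at onset: "TEAEs will be attributed to the dose level where the adverse event start date is on or after the start date" of that level and before the next one. A patient counts once per dose level for each term. The footnotes to the Table B.14.3.1 series say: "Percentages are based on the number of patients in each dose group and overall". Episode counts and a post-last-dose column are also shown. Section 5.3.1 states "Study drug exposure will be summarized by dose level", but in a separate table, and duration is not used as a denominator. Kaplan-Meier estimates are planned for efficacy events (5.4.2.2), not for adverse events. Section 2.2 has escalation from 400 mg qd to "400 mg bid allowed at or after the Week 3 visit for insufficient clinical response", and to 600 mg bid from Week 5.

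Section 3.4.3 gives treatment-emergent events no end. The table footnotes end them before the last-dose date and start post-last-dose events after the last dose.

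**Part A.** SAP 9.1: "A treatment-emergent AE (TEAE) is defined as an AE that begins on or after the first dose of study drug". Events are collected to the end of the study, which is 12 weeks on drug followed by 12 weeks off (SAP 3.1). There is no post-last-dose column, and patients are grouped by the maximum dose they received.

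**The concern.** Protocol 2.3 gives a reason to read safety by dose: "It is possible that a lower, once daily dose may have a greater benefit-risk relationship". A reader of the Part B tables will look across the dose columns for that answer. If one column reflects 2 weeks per patient and another 20, the percentages mix the event rate with the length of observation, and a difference can appear or vanish for that reason alone.

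In Part A the stated objective is "To evaluate the clinical safety of PRN1008 in patients with PV over a 12-week" treatment period, yet the counting window for a completer is about twice that. Off-drug events are merged with on-drug events, and the tables do not separate them.

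**Working it through.** **No safety figure to reproduce.** Neither document states an expected adverse event rate or a safety precision. The only design figure concerns efficacy and reproduces: 1.2816 × √(0.5 × 0.5 / 25) = 0.128, the stated ±13%.

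**Planned time at each level in Part B** (visit days from the schedule):

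- 400 mg qd: (15 − 1)/7 = 2 weeks to (169 − 1)/7 = 24 weeks. The ±3-day visit window makes the minimum 11 to 17 days.
- 400 mg bid after escalation: (29 − 15)/7 = 2 weeks to (169 − 15)/7 = 22 weeks.
- 600 mg bid after escalation: at most (169 − 29)/7 = 20 weeks.
- Post last dose: (197 − 169)/7 = 4 weeks.

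**Assumptions.** The weekly hazard h of a first event within a level is constant and the same at every dose and after the last dose. Half the patients escalate once, half of those escalate again, and there is no dropout. The dose-group denominator is everyone who received that dose. Crude risk over t weeks is 1 − exp(−ht).

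*Early steps (Weeks 3 and 5), h = 0.05:*

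- qd: 0.5(1 − e^−0.1) + 0.5(1 − e^−1.2) = 39.7%
- 400 mg bid: 0.5(1 − e^−0.1) + 0.5(1 − e^−1.1) = 38.1%
- 600 mg bid: 1 − e^−1.0 = 63.2%
- post last dose: 1 − e^−0.2 = 18.1%

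*Late steps (Weeks 13 and 17), h = 0.05.* Times are 12 or 24 weeks on qd, 4 or 12 on 400 mg bid, and 8 on 600 mg bid:

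- qd: 0.5(1 − e^−0.6) + 0.5(1 − e^−1.2) = 57.5%
- 400 mg bid: 0.5(1 − e^−0.2) + 0.5(1 − e^−0.6) = 31.6%
- 600 mg bid: 1 − e^−0.4 = 33.0%

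The same formulas at other hazards give:

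| h per week | Early: qd / 400 bid / 600 bid / post | Late: qd / 400 bid / 600 bid |
|---|---|---|
| 2% | 21 / 20 / 33 / 8% | 30 / 15 / 15% |
| 5% | 40 / 38 / 63 / 18% | 57 / 32 / 33% |
| 10% | 55 / 54 / 86 / 33% | 80 / 51 / 55% |

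**Part A, h = 0.05 on drug.** The 12-week on-treatment risk is 1 − e^−0.6 = 45%. Over the 24 weeks counted, with the off-drug hazard at a fraction m of the on-drug hazard, the reported risk is 1 − exp(−0.6 − 0.6m): 70% (m = 1), 59% (m = ½), 53% (m = ¼) and 45% (m = 0).

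**Which denominator repairs it.** Dividing first events by total time at dose (the 5.3.1 duration) does not. In the early scenario the mean durations are 13, 12, 20 and 4 weeks, giving 0.397/13, 0.381/12, 0.632/20 and 0.181/4, that is 3.1, 3.2, 3.2 and 4.5 per 100 patient-weeks from equal hazards. If time stops at the first event, expected time is (1 − e^−ht)/h per patient and every column returns 5 per 100.

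**The case against.** The strongest reply is that the primary outcome is incidence without a dose comparison, and that the Overall column has one planned window within each Part. That stands. A reader might infer that the primary safety rates as a whole lack a common time at risk; the documents support this only for the dose-level columns and for a Part A against Part B reading.

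A reader might also infer a built-in dose trend. That is not supported: with early steps qd and 400 mg bid are nearly equal, and with late steps qd is highest. Nor is pooling of safety data planned. Combining the Parts is mentioned for clinical activity and efficacy, and the different grouping rules (maximum dose against dose at onset) would keep the dose columns from aligning anyway.

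Part B's episode counts, exposure table and listings let a careful reader approximate event rates by hand. The analysis is descriptive, with no hypothesis tests. Small groups limit what rates can show: under the fractions above, 600 mg bid holds about 25 × 0.5 × 0.5 ≈ 6 patients, and 4 of 6 has an exact 95% interval of 22% to 96%. Finally, the received-at-least-once rule is explicit only for efficacy (Part B SAP 5.4). For safety it is an assumption here, and the treatment-group section (3.3) was not in the text available.

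These points narrow the concern. They do not put the dose columns on equal time at risk.

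**Conclusion.** The point holds for the Part B dose-level and post-last-dose columns and for Part A's open-ended definition. Part B columns can differ through time at risk alone, by tens of percentage points in the scenarios shown; size and direction depend on when and how many patients escalate, which cannot be known in advance. In Part A about half of a completer's window is off drug, and the effect ranges from nothing to 45% read as 70%. The 70% figure requires an equal off-drug hazard, which the documents do not establish. All hazards and escalation fractions are assumptions. The consequence is a misleading descriptive table, not a wrong test, and the change is worth making because it is cheap.

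**What to change.** (a) In Tables B.14.3.1.1 to B.14.3.1.3, B.14.3.1.6 and B.14.3.1.7, add patient-weeks at risk for each dose level and post last dose, and first-event incidence per 100 patient-weeks with an exact Poisson 95% CI. Censor each patient's time in a level at the first event; do not use the total duration from 5.3.1. State that the rates are descriptive, remain confounded because escalation follows insufficient response, and will be imprecise in small groups.

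(b) Reconcile Part B SAP 3.4.3 with the table footnotes. As written, an event starting on the last-dose date falls in neither footnote category, while under 3.4.3 an event after the last dose is both treatment-emergent and post last dose. Each event should be counted once.

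(c) Because the last Part A patient finished in June 2019 (Part B SAP 1), provide supplementary Part A output that splits treatment-emergent events into on-treatment (first dose through last-dose date) and post-last-dose (after that date).

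The cost is SAP wording, some programming and wider tables. The dates are already collected, and no patient procedure changes.
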